9.4.4 BASELINE DESCRIPTIVE STATISTICS

Intervention groups will be compared on the proportion of discharge opioid prescriptions above guidelines, proportion of discharges with any opioid prescription, and average discharge opioid prescription quantity during the baseline period (1 June 2020 through 18 October 2021).

9.4.5 PLANNED INTERIM ANALYSES

Any interim analyses conducted during the intervention period will be solely for the purposes of safety monitoring or planning related studies; the intervention will not be altered unless recommended by the study's Data Safety and Monitoring Board.

9.4.6 SUB-GROUP ANALYSES

We will test for heterogeneity in the treatment effect along several domains. Specifically, we will add terms interacting characteristics of the surgeon with each intervention arm and conduct an F-test of the interaction terms for each nudge.

- Specialty: We will also conduct analyses to test whether the response to each nudge varies by surgeons' specialty.
- Volume of surgeries: We will test for heterogeneity by number of surgeries performed over the 12 month study period. We will only include surgeries for which we have guidelines in this count.
- Baseline opioid prescribing: We will categorize surgeons based on the portion of their surgeries in the 12 months prior to the start of the intervention that were above guidelines. We expect that the intervention will have a larger effect for surgeon with a higher share of prescription above guidelines.

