5.5 STRATEGIES FOR RECRUITMENT AND RETENTION

We will enroll surgeons by screening all surgeons present in electronic health record data from 1 June 2020 through 31 May 2021, and a waiver of informed consent has been granted by the RAND IRB, so surgeon-level recruitment is unnecessary. Hospitals have been recruited and will be retained through communication with hospital- and system-level administrators.

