6 STUDY INTERVENTION

6.1 STUDY INTERVENTION(S) ADMINISTRATION

6.1.1 STUDY INTERVENTION DESCRIPTION

Surgeons randomized to our study intervention will receive one of two types of behavioral nudges delivered as monthly emails. The two nudges will be active for twelve months (October 2021–October 2022).

To ensure that the nudges target only *inappropriate* opioid prescribing, surgeons will receive nudges only when they write opioid prescriptions that exceed post-operative opioid prescribing guidelines developed by multidisciplinary teams at the Mayo Clinic.^{32, 46, 47} (and personal communication with [name], Ph.D., MPH, on opioid prescribing guidelines for caesarean section, March 12, 2021; unreferenced) These guidelines recommend ranges of 5mg oxycodone tablet quantities specific to the procedure performed and are partly based on patient surveys of actual post-operative opioid use.

In both nudge conditions, eligibility for receiving a monthly nudge is contingent upon at least two of the surgeon's patients being discharged with a post-operative opioid prescription exceeding the quantities specified by the Mayo Clinic guidelines. Though it may seem counterintuitive for the descriptive norm nudge to be based implicitly on prescribing guidelines, this choice ensures patient safety and avoids confounding the content of the nudge with the threshold for receiving a nudge.

Intervention arm 1: nudge based on descriptive norms

Surgeons randomized to this condition will receive an email with the following content at the end of each month in which at least two of their patients are discharged with a post-operative opioid prescription that exceeds the prescribing guideline for the procedure performed.

[Subject line: Your peers vs. your opioid prescribing safety record]

Dear Dr. [Name],

In an effort to reduce opioid use among our surgical patients, Sutter Health is reviewing opioid prescriptions and prescribing patterns for surgeons and will be communicating the findings.

In [month], at least **XX** of your patients were discharged with opioid prescriptions **exceeding** the amount prescribed by **YY%** of your peers for these procedures.

YY% of [specialty] surgeons at Sutter Health prescribe within the ranges below.

We will continue to send you opioid prescribing safety reports.

Sincerely,

[Signature(s) of chief medical executive, chief of staff, and/or surgical department chair at the surgeon's hospital]

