In the binary outcome version, the parameters β_1 and β_2 again identify the treatment effects of arms 1 and 2 relative to the control arm, with interpretation of these parameters adjusted relative to the link function implemented.

Longitudinal analysis

In addition to assessing the treatment effect averaged over the entire 12-month period, we will also analyze treatment effects by month to assess how the treatment effect evolves over time. For this analysis, we will interact study month indicators with the treatment assignment indicators.

Persistence analysis

We will conduct a secondary analysis to examine whether nudge effects persist once the nudges are discontinued. The data will include the RCT data analyzed in the model above, but also data collected for one year post-intervention (the "persistence period"). The analysis model above will be modified by adding an indicator for the RCT period versus persistence period plus interaction terms for period and each nudge to the model. The statistical significance of these interaction terms will be used to assess whether the treatment effect significantly differs post-RCT.

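### The surgeon-volume subgroup is counted during the study year, after assignment, although the same count is available from the baseline period.

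*Combined protocol and SAP*

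**What the plan says.** Section 9.4.6 (Sub-Group Analyses) treats each subgroup variable as a feature of the surgeon: "we will add terms interacting characteristics of the surgeon with each intervention arm and conduct an F-test of the interaction terms for each nudge". Three variables follow: specialty, volume and baseline prescribing.

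- **Volume:** "We will test for heterogeneity by number of surgeries performed over the 12 month study period". The count is restricted by procedure type: "We will only include surgeries for which we have guidelines in this count".
- **Baseline prescribing:** surgeons are grouped by the share of their operations that exceeded guideline quantities, and the window is stated as "in the 12 months prior to the start of the intervention".

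The analysis section (9.4.2, longitudinal analysis) refers to the main analysis window in similar terms: "In addition to assessing the treatment effect averaged over the entire 12-month period". Section 1.3 schedules nudges for the third Tuesday of each month from October 2021 through September 2022.

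Baseline data are described in three places. Section 9.4.4 sets a baseline period of 1 June 2020 through 18 October 2021. Section 5.5 enrols surgeons from "electronic health record data from 1 June 2020 through 31 May 2021". Section 5.2 uses procedure counts from that same year to exclude surgeons who work across specialties.

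**The concern.** A subgroup comparison keeps the protection of randomisation when surgeons are classified by something fixed before the intervention could act. Study-year volume is not fixed in that way.

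1. **Comparability.** If nudges altered how many guideline-covered operations some surgeons perform, or if departures differed by arm, surgeons in a given volume level would no longer be comparable across arms. The interaction would then partly reflect who was sorted into each level.
2. **Interpretation.** Even if departures are unrelated to arm, a surgeon who leaves halfway through is counted as low volume and contributes only early-month discharges. Low volume then partly means short exposure. Section 7.3 marks loss to follow-up as not applicable, so no rule covers such surgeons.

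At stake is the reading of one interaction test per nudge. Volume bears on how often a nudge can be sent, since "eligibility for receiving a monthly nudge is contingent upon at least two of the surgeon's patients" exceeding the guideline quantity at discharge. A finding that response depends on volume would therefore attract interest, and it should rest on a variable the trial could not have affected.

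**Working it through.** The plan gives no figure on this point to reproduce. The power statement in 9.2 concerns the pairwise arm comparisons. The check therefore covers dates, then an illustration with assumed inputs.

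**Step 1: when the count is taken.** Tuesdays in October 2021 fall on the 5th, 12th and 19th, so the first nudge is on 19 October 2021, the day after the 9.4.4 baseline period ends. A 12-month study period starting there lies wholly after assignment. The synopsis also gives a 24-month study duration, so the wording is loose, but neither reading turns the count into a baseline one.

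**Step 2: whether a baseline count exists.**
- 1 June 2020 to 31 May 2021: 365 days.
- 1 June to 18 October 2021: 30 + 31 + 31 + 30 + 18 = 140 days.
- Baseline period: 365 + 140 = 505 days.
- 12 months before the first nudge, 19 October 2020 to 18 October 2021: 505 − 140 = 365 days, wholly inside the baseline period.

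The baseline-prescribing subgroup uses the proportion of a surgeon's surgeries above guideline in the year before the intervention. Its denominator is essentially the count needed here.

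**Step 3: size of the comparability problem (assumed inputs).** A simulation of 400,000 surgeons in two arms, with no true heterogeneity, assumed:
- an arm effect of −0.05 on the above-guideline share;
- a between-surgeon SD of 0.10;
- log-volume with SD 0.6, split at the median;
- counted volume lowered by a given percentage only in nudge-arm surgeons with above-average prescribing.

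The table shows the effect in high-volume minus low-volume surgeons, which should be zero.

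| Assumed fall in counted volume | Baseline split | Study-period split | Study-period result ÷ (−0.05) |
|---|---|---|---|
| 0% | 0.0004 | 0.0004 | about 0 |
| 5% | −0.0000 | −0.0052 | 10% |
| 10% | −0.0002 | −0.0114 | 23% |
| 20% | −0.0013 | −0.0248 | 50% |

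Each arm-by-volume cell holds about 100,000 surgeons, so the simulation standard error is about 2 × 0.10/√100,000 = 0.0006. The baseline column is within roughly two standard errors of zero. Negative values make the nudge look stronger in high-volume surgeons. Nothing in the documents indicates that any row but the first applies.

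**Step 4: the exposure-time problem.** A surgeon with a steady caseload who leaves after 6 months has 6/12 = half the count. Suppose, for illustration, that the effect grows in proportion to the study month. The mean month is then (1 + 6)/2 = 3.5 for the leaver and (1 + 12)/2 = 6.5 for a full-year surgeon. The leaver's average effect is 3.5/6.5 = 54% of the full-year one, with no dependence on caseload. If the effect faded instead, the distortion would run the other way; if it were constant, there would be none. The plan treats the time course as open, since 9.4.2 estimates effects by month.

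**The case against.** The strongest reply is that a monthly email about opioid quantities gives a surgeon no reason to perform more or fewer operations. With volume unaffected, the first row of the table applies and there is no bias. Departures would have to differ by arm to damage comparability, and nothing suggests that they will. The two windows can also be defended: prescribing must be measured before the intervention because it is the outcome, whereas volume is not an outcome, and study-year volume describes the opportunity to be nudged. A baseline count has flaws too, because a surgeon who joined part-way through has a truncated one.

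Much of this stands. The likely bias is small, different windows are not in themselves a contradiction, and study-year volume has descriptive use. The reply does not remove the exposure-time problem, which needs no effect of the arm on volume or departures. Nor does the plan itself give any reason for the later window.

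Two stronger readings are tempting and are not supported:

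- **That the nudge itself lowers the count.** Section 5.1 frames eligibility around oral opioid prescriptions, so a reader might infer that volume is a count of prescriptions. But 9.4.6 counts surgeries that have a guideline. Section 9.4.2 keeps discharges without an opioid in the data, coded as within guideline. The safety reports in 8.2 likewise distinguish all patients meeting the inclusion criteria (Report 1) from those prescribed an opioid (Report 3).
- **That the two-discharge trigger biases the comparison, or makes volume the headline subgroup.** The trigger links volume to exposure, which is not bias. The only subgroup given an expected direction in 9.4.6 is baseline prescribing.

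**Conclusion.** The point holds in a limited form. The volume moderator is measured after assignment, the plan does not justify this, and an equivalent count taken before the first nudge is available.

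Its size cannot be estimated from the documents. If nudges change neither case volume nor departures, the comparability bias is nil. What remains is the mixing of volume with length of exposure, which depends on how many surgeons work only part of the year and on how the effect changes by month. The non-zero simulation results show what assumed volume shifts would do; they do not predict this trial.

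A reader might go further and infer that the trial's main result is at risk. It is not: the primary estimate does not use this variable, and the consequence is confined to one subgroup test for each nudge.

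**What to change.** In 9.4.6, define volume as the number of guideline-covered surgeries, with or without an opioid prescribed at discharge, that the surgeon performed in the 12 months before the first nudge (19 October 2020 to 18 October 2021). This matches the window of the baseline-prescribing subgroup. Use this count as the moderator in both nudge interactions. Keep the study-period count, if wanted, only as a labelled descriptive or sensitivity analysis.

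The documents do not give the date of randomisation. What matters is that the window closes before any email is sent. If a count that also matches the screening records is preferred, 1 June 2020 to 31 May 2021 would serve.

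The cost is one SAP sentence and no data beyond the stated baseline period. The drawbacks are small: baseline volume may differ from study-year volume for some surgeons, and those who joined part-way through the window will have truncated counts.

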9 STATISTICAL CONSIDERATIONS

9.1 STATISTICAL HYPOTHESES

The null hypotheses are that (1) $\beta_1 = 0$, (2) $\beta_2 = 0$, and (3) $\beta_1 = \beta_2$ in the hierarchical linear model

$$Y_{ipsh} = \beta_0 + \beta_1 ARM1_{sh} + \beta_2 ARM2_{sh} + \gamma_{1h} ARM1_{sh} + \gamma_{2h} ARM2_{sh} + \omega_1 X_{ipsh} + \omega_2 Z_{psh} + \omega_3 U_{sh} + \omega_4 W_h + \gamma_h + \eta_{sh} + \varphi_{psh} + \varepsilon_{ipsh}, \quad (1)$$

where i is the patient treated by surgeon p in specialty s at hospital h , $ARM1_{sh}$ and $ARM2_{sh}$ are indicator variables for whether specialty s at hospital h were assigned to intervention arm one or two respectively, X is a set of patient covariates, Z is a set of surgeon covariates, U is a set of specialty covariates, and W is a set of hospital covariates.

The alternative hypotheses are that (1) $\beta_1 \neq 0$, (2) $\beta_2 \neq 0$, and (3) $\beta_1 \neq \beta_2$.

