9.2 SAMPLE SIZE DETERMINATION

Statistical power to identify effects of the nudges was examined using recent past data from the participating hospitals. We estimated design parameters required by the PowerUpR package in R software,⁴⁸ which provides the capability to estimate statistical power for randomized block clustered designs. Examining medication dose, input parameters for the calculation included unconditional intracluster correlations (ICC) for the hospital (ICC=0.005), service line (ICC=0.039), and provider (ICC=0.337) levels; the number of service line groups (up to three per hospital); the number of providers by service line expected to participate in the study; and number of patients per service line. The ICCs were empirically determined from our preliminary data. We assumed that covariates informative of the dosage would explain between 25 percent and 50 percent of the dosage variation at each of the patient, provider, and service line levels (i.e., R^2 between 0.25 and 0.50). We derived statistical power, assuming one third of the service line groups within hospital will be randomly assigned to each study arm (two treatment and one control). We computed power for pairwise comparison of each of the two nudge arms versus the no nudge arm and adjusted our alpha level to account for multiple comparisons (alpha=0.05/2). We will have 80% power to detect significant differences between the intervention conditions of at least a minimum detectable effect size (MDES) = 0.347 standard deviations (SDs) when $R^2=0.25$, while $R^2=0.5$ would yield a MDES of 0.305.

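### The baseline-prescribing subgroup analysis groups a continuous share at unstated cut-points; a continuous interaction test would use the data better if the gradient is roughly linear

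*Combined protocol and SAP*

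**What the plan says.** Section 9.4.6 lists three possible effect modifiers: specialty, surgical volume and baseline opioid prescribing. For each, terms crossing the surgeon characteristic with the arms are added to the model, and the plan will "conduct an F-test of the interaction terms for each nudge".

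For baseline prescribing it says "We will categorize surgeons based on the portion of their surgeries in the 12 months prior to the start of the intervention"; the portion meant is the one exceeding the guideline. It then predicts a direction: "We expect that the intervention will have a larger effect for surgeon with a higher share of prescription above guidelines". No direction is given for specialty or volume, and the volume item does not call for categories.

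No section states how many groups there will be, where the cuts fall, when they will be fixed, or whether the share will also be analysed uncut.

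The only power statement is in Section 9.2 and concerns main effects: "We computed power for pairwise comparison of each of the two nudge arms versus the no nudge arm". It was worked out for medication dose, at an alpha of 0.05/2. No power is given for any interaction, and no alpha is stated for the subgroup tests.

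**The concern.** The modifier is a proportion between 0 and 1 that can be computed from the health-record data the trial already uses. The plan expects the effect to grow with it. Grouping treats all surgeons within a group as alike, so the within-group variation no longer helps to detect a gradient. With more than two groups, an F-test of the interaction terms also spreads one directional idea over several degrees of freedom. A real gradient would then be more easily missed and reported as no heterogeneity.

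A second problem does not depend on power. If the number of groups and the cut-points are open, they can be settled after results are visible, and the choice can change the answer. Section 6.3 blinds most investigators to assignment, which reduces this risk. Nothing ties the choice of cuts to a time before unblinding.

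**Working it through.** **The plan's own figure.** There is none for this test. The 80% in Section 9.2 belongs to the main-effect comparisons (minimum detectable effect 0.347 SD at R² = 0.25 and 0.305 SD at R² = 0.50). It cannot be reproduced, because surgeons and patients per service line are named as inputs without values. What follows is therefore an illustration of relative loss.

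**Assumptions, none of them in the documents.** The gradient is linear in the share. A continuous one-df interaction has 80% power at two-sided 5%. Information is proportional to the variance of the modifier that the analysis retains. A large-sample chi-square stands in for the F-test.

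**Step 1: noncentrality of the continuous test.**
λ = (1.960 + 0.842)² = 7.85.

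**Step 2: information kept by grouping.**
e = between-group variance of the share ÷ total variance.
- Normal share, median split: e = 2/π = 0.637.
- Uniform share, median split: group means 0.25 and 0.75 give variance 0.0625; total variance is 1/12; e = 0.75.
- Tertiles: e = 0.793 (normal) and 0.889 (uniform).

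**Step 3: power after grouping.** Use the noncentral chi-square with noncentrality e·λ and df = groups − 1. For two groups this is Φ(√e × 2.802 − 1.960).
- Normal, median split: Φ(0.798 × 2.802 − 1.960) = Φ(0.276) = 61%.
- Uniform, median split: Φ(0.866 × 2.802 − 1.960) = Φ(0.467) = 68%.
- Tertiles, 2 df: noncentrality 6.22 gives 60% (normal); 6.98 gives 65% (uniform).

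**Step 4: other choices the plan permits, same 80% start.**

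| Grouping | Normal share | Uniform share |
|---|---|---|
| Median split, 1 df | 61% | 68% |
| Tertiles, 2 df | 60% | 65% |
| Quartiles, 3 df | 57% | 61% |
| Tertiles as a 1-df trend | 70% | 75% |
| 80/20 split | 50% | 49% |
| 90/10 split | 37% | 31% |

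The distribution of the share also matters. A median split gives 59% for Beta(1,4), 56% for Beta(0.5,2) and 71% for the U-shaped Beta(0.5,0.5). Unequal cuts are not always worse: for the two skewed shapes an 80/20 split gives 62% and 66%.

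**Step 5: other starting points, median split (normal to uniform).** A start of 90% falls to 73–80%, 50% to 35–40%, and 30% to 21–24%. With alpha 0.025 and an 80% start, the result is 59–67%.

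**Step 6: if the gradient is not linear.** Suppose the true effect is a step, and a split exactly at the step has 80% power. A linear term then has 61–68% if the step is at the median, and 49–50% if it is at the 80th percentile (uniform and normal shares). The ranking of the two tests is reversed.

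**The case against.** The strongest counter-argument is about shape. The plan predicts a direction, not a straight line. Section 6.1.1 sends an email only when at least two of a surgeon's patients in a month exceed the guideline, so surgeons with low shares may receive little or no intervention. The primary outcome is binary and modelled with a logit link. A threshold-like effect is therefore plausible, and Step 6 shows that a well-placed split would then beat a linear term.

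This stands as a limit on the claim. A reader might infer that the planned test is weaker whatever the truth; the documents do not support that, because they do not give the shape. It does not rescue the plan as written, for two reasons. Groups win only if an unstated cut lands near the step. And the trigger is a monthly count that corresponds to no single share: two of 4 eligible discharges is 50%, two of 40 is 5%. A continuous term with a check for curvature covers more of the plausible shapes.

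Three smaller objections also stand:
- With two groups, or with an ordinal trend score, the test has one df, so the loss from extra degrees of freedom is conditional.
- A baseline share need not exist for every surgeon. Section 5.5 screens on records from 1 June 2020 to 31 May 2021, whereas the share covers the 12 months before the intervention and needs procedures that have a guideline.
- A reader might infer that this analysis decides whether nudges should be aimed at high prescribers. No section says so; Section 4.2 frames the policy question as whether health systems should invest in such nudges.

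**Conclusion.** The point holds in a limited form. The plan groups a continuous modifier without stating groups or cut-points, while predicting an effect that rises with it. Under a roughly linear gradient this loses information: a median split keeps 64–75% of it for normal to uniform shares. For a gradient that the continuous test would detect with 80% power, that means about 61–68% power, or about 60–65% with tertiles on two df.

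These figures rest on an assumed starting power, an assumed distribution, assumed cuts and linearity. A reader might set them beside the 80% in Section 9.2 and conclude that grouping lowers this trial's power from 80% to the 60s. The documents do not support that: their 80% is for main effects on dose, and the actual power of this interaction cannot be computed from them.

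The open cut-points are a weakness whatever the power. The consequence is confined to one of three subgroup analyses; the primary and secondary effect estimates are untouched.

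**What to change.** In Section 9.4.6:

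1. Make the test of this modifier a centred continuous baseline above-guideline share, entered as a main effect plus an arm-by-share interaction with one df per nudge.
2. Pre-specify a quadratic or spline term as the check on linearity.
3. Report the fitted effect of each nudge at set percentiles of the share, for example the 10th, 50th and 90th.
4. Use groups for display only, with their number and cut-points fixed before unblinding.
5. State how surgeons with no eligible surgeries in the 12-month baseline window are handled.

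The cost is a change of wording, with no new data. The downside is the linearity assumption, which item 2 addresses.
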